7.2. Covariates and Subgroups

7.2.1. Planned Covariates

No covariates are planned for this study.

7.2.2. Planned Subgroups

No subgroups are planned for this study.

7.3. Management of Analysis Data

7.3.1. Data Handling

Unscheduled or repeated laboratory results will not be analyzed for the summary of continuous values but will be included in the laboratory shift tables as follows. Unscheduled tests will be included with the time of the nearest regularly scheduled test. If there is a scheduled test and one or more unscheduled tests assigned to the same time point, the most conservative test (i.e., a test with low or high results) will be used. Repeated tests will be included only if they reflect abnormal (low or high) results and the corresponding original results are normal. All laboratory values, for all visits, will be provided in by subject listings.

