9.5 Clinical Laboratory Tests

A central laboratory will be used for this study. Blood draws for chemistry and hematology tests and urine samples for urinalyses will be collected and sent to the central laboratory. Table 4 presents the specific clinical laboratory tests to be evaluated.

All laboratory values that are outside of the normal range for that parameter will be so flagged when reported to the site. The investigator will annotate laboratory reports to indicate whether any abnormal laboratory value is considered clinically significant. Any abnormal laboratory value that is considered clinically relevant should be confirmed by a repeated laboratory test when possible. If a clinically significant laboratory abnormality requires treatment or is the reason for a subject being discontinued from the study, the abnormal result must be classified as an AE. If clinically relevant and considered an AE, the event must be followed until resolution or as long as medically necessary and be recorded on the AE page of the eCRF.

Table 4: Clinical Laboratory Tests, Study OS440-3005

Hematology	Urinalysis	Serum Chemistry
Hematocrit	Bilirubin	Alanine aminotransferase (ALT)
Hemoglobin	Blood	Albumin
Platelet count	Glucose	Alkaline phosphatase
Red blood cell (RBC) count	Ketones	Aspartic acid transaminase (AST)
White blood cell (WBC) count with differential	Leukocytes esterase	Bicarbonate
	Specific gravity	Blood urea nitrogen (BUN)
	Color	Chloride
	pH	Creatinine
	Protein	Creatinine kinase
	Microscopic examination of urine:	Glucose
	• Epithelial cells	Potassium
	• Casts (RBC, WBC, etc.)	Sodium
	• Red blood cells	Total bilirubin (if elevated, obtain direct bilirubin)
	• White blood cells	Uric acid
	Urine pregnancy test (at the site)	

ALT = alanine transaminase; AST = aspartate transaminase; BUN = blood urea nitrogen; RBC = red blood cell; WBC = white blood cell

Samples for clinical hematology, serum chemistry, and urinalysis will be obtained for each subject and sent to a central laboratory at the visits specified in Table 1. Site personnel will do a routine urinalysis by dipstick on site and the central laboratory will do a complete microscopic urine examination. Site personnel will also complete a urine pregnancy test for female subjects of childbearing potential on site at the visits specified in Table 1 (see [Section 7.8](#) regarding serum pregnancy testing in premenopausal women of childbearing potential at Baseline [Screening for *de novo* subjects]).

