10.3. Clinical Laboratory Evaluations

Clinical Laboratory results will be summarized descriptively by time point for the observed value as well as for the change from baseline value. In addition, laboratory shift tables will be provided for all laboratory parameters where low/normal/high or abnormal/normal status can be ascertained. Listings of individual laboratory parameters by visit with normal ranges and abnormality assessments will also be completed by subject.

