10.4. Vital Signs

Vital sign results will be summarized descriptively by time point for the observed value as well as for the change from baseline value. All vital sign data by subject will be presented in a listing. Unscheduled visit results will not be summarized but will be included in subject data listings.

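### The size of an extreme unscheduled or repeat laboratory value appears in no planned laboratory table, and SAP 10.3 omits the abnormality count that Protocol 11.5 promises

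*SAP*

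**What the plan says.** SAP 7.3.1 sets three rules for laboratory results outside the scheduled set.

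- **Numeric summaries.** "Unscheduled or repeated laboratory results will not be analyzed for the summary of continuous values".
- **Unscheduled tests in shift tables.** "Unscheduled tests will be included with the time of the nearest regularly scheduled test". Where one shares a time point with a scheduled test, "the most conservative test (i.e., a test with low or high results) will be used".
- **Repeats in shift tables.** "Repeated tests will be included only if they reflect abnormal (low or high) results and the corresponding original results are normal".

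All values also go into listings. SAP 10.3 plans two kinds of laboratory table: descriptive summaries by time point (observed value and change from baseline), and shifts, where "laboratory shift tables will be provided for all laboratory parameters where low/normal/high or abnormal/normal status can be ascertained". SAP 7.4.1 puts the minimum and maximum among the descriptive statistics.

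Protocol 9.5 describes how repeats arise: "Any abnormal laboratory value that is considered clinically relevant should be confirmed by a repeated laboratory test when possible". Protocol 11.5 promises, besides the shifts, a count and percentage of subjects who develop laboratory abnormalities on treatment. SAP 10.3 does not list that table, although SAP 3.3 says the SAP's analyses agree with the protocol's.

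For vital signs, SAP 10.4 says: "Unscheduled visit results will not be summarized but will be included in subject data listings". It plans no vital-sign shift table.

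**The concern.** Long-term safety is the primary objective. Samples drawn for cause, or drawn to confirm an abnormal result, are a natural place for a large excursion to show itself. Under these rules such a sample contributes at most a category. A value just above the upper limit and one ten times the limit count the same, and the printed maximum comes from scheduled originals alone.

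The repeat rule also sits badly with Protocol 9.5. The protocol generates repeats mainly when the original is abnormal, and the SAP admits a repeat only when the original is normal. Most repeats the protocol asks for will therefore stay out of the tables, including any that are much worse than the original.

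**Working it through.** The documents give no figure to reproduce here, so the check applies the rules of SAP 7.3.1 case by case.

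**1. Repeat rule.** Original and repeat can each be Low, Normal or High, giving 3 × 3 = 9 pairs.

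| Original, then repeat | Pairs | Repeat enters shift table? | Abnormal category lost? |
|---|---|---|---|
| Normal then Low; Normal then High | 2 | Yes | No |
| Any original, then Normal | 3 | No | No |
| Low then Low; High then High | 2 | No | No, already counted through the original |
| Low then High; High then Low | 2 | No | Yes, the repeat's category |

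The repeat enters in 2 of 9 pairs. Of the 7 excluded pairs, 3 + 2 = 5 lose no abnormal category and 2 do.

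**2. Unscheduled rule.** Pairing a scheduled with an unscheduled result at the same time point again gives 9 cases. In 7 the rule yields a clear category, abnormal whenever either result is abnormal. In the 2 opposite-direction cases the SAP does not say which result wins.

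**3. Magnitude.** The values below are assumed for illustration, with an upper limit of 40.

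| Scheduled or original | Other sample | Subject's value in the numeric table | True highest value | Shift category |
|---|---|---|---|---|
| 38 | 400 (unscheduled) | 38 | 400 | High |
| 90 | 400 (repeat) | 90 | 400 | High |
| 400 | 90 (repeat) | 400 | 400 | High |

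In the first two rows the category is right, but the value of 400 (400/40 = 10 times the limit) is in no table. In the third row the extreme is a scheduled value, so it can be printed as the maximum.

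**4. Promised and planned laboratory tables.**

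| Table | Protocol 11.5 | SAP 10.3 |
|---|---|---|
| By-visit descriptive summary | Yes | Yes, scheduled originals only |
| Normal-range shifts | Yes, baseline to end of study | Yes, time points not stated |
| Count of subjects with treatment-emergent abnormalities | Yes | Not listed |
| Worst on-treatment value or threshold crossing | No | No |

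**5. Vital signs.** SAP 10.4 excludes unscheduled-visit results from summaries and has no shift table, so not even a category is carried. Protocol 9.2 takes supine and standing blood pressure specifically to look for orthostatic hypotension. A reading taken at an unscheduled visit for dizziness would reach no vital-sign table.

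**The case against.** The other side has several sound points.

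- **The rules are conservative by category.** An abnormal original stands, a normal repeat cannot erase it, and an abnormal unscheduled result displaces a normal scheduled one. This stands.
- **Serious abnormalities have another route.** Under Protocol 9.5, a clinically significant abnormality that is treated or leads to discontinuation must be recorded as an adverse event, so it reaches the adverse event tables if treatment-emergent. This stands, but those tables show term and severity, and Protocol 9.7.2.3 grades severity by effect on function. A large rise without symptoms could be graded mild.
- **Other safeguards exist.** The DSMB looks at clinically important laboratory values, early-termination data are assigned to scheduled visits (SAP 7.3.3), everything is listed, and SAP 10.6 allows further safety analyses. None of these is a planned tabulation of size. A table chosen after the results are seen is also weaker than a prespecified one.
- **The SAP does not separate repeated from unscheduled tests.** A confirmatory sample on a later day might fall under the unscheduled rule. That would affect its category, but its size is excluded from the numeric tables either way.
- **The vital-sign rule is narrower.** It covers unscheduled visits and is silent on repeats. This stands.

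A reader might infer that the most extreme on-drug values appear in no table at all. The documents do not support that: scheduled extremes are printed as minimum or maximum, and unscheduled results do enter the shift tables. A reader might also try to size the problem from the gaps between scheduled draws (Weeks 6, 14, 28, 42 and 54). Any such figure would need an assumed length and timing of excursion. It would describe the protocol's visit schedule, not the effect of SAP 7.3.1, and no new table recovers a value that was never sampled.

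**Conclusion.** The concern holds in a limited form. The size of an extreme unscheduled or repeat laboratory value is in no planned laboratory table. Its category is usually kept, with loss in 2 of 9 repeat pairs and an undefined outcome in 2 of 9 unscheduled pairs. These are counts of possible patterns, not frequencies: opposite-direction pairs may be rare, and the documents give no rate of unscheduled or repeat sampling. Separately, the count promised in Protocol 11.5 is missing from SAP 10.3, and unscheduled-visit vital signs reach no summary.

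That the category is kept assumes shift tables by visit, as SAP 7.3.1 implies. If only the baseline-to-end-of-study shift of Protocol 11.5 is produced, mid-study categories would be missed too, because the Week 60 draw follows the taper of Weeks 54 to 56.

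This is a gap in presentation, worth closing because it touches the primary objective and is cheap to close. It is not evidence that a signal has been hidden.

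**What to change.** 1. Leave the by-visit laboratory summaries on scheduled samples, as SAP 7.3.1 has them.
2. Add to SAP 10.3 a table of each subject's highest and lowest on-treatment value from all samples (scheduled, unscheduled and repeat), whatever the original result was. Include n (%) by multiple of the normal limit for key analytes such as ALT, AST, total bilirubin, creatinine and creatine kinase. State the on-treatment window; the first-to-last-dose window in SAP 10.1 would serve.
3. Add the Protocol 11.5 count of subjects with treatment-emergent laboratory abnormalities, built from the same data.
4. Add to SAP 10.4 a summary of each subject's highest and lowest on-treatment vital signs that includes unscheduled visits.

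The cost is SAP wording and one or two extra table programs. The values are already due to appear in the listings, so no new data collection is needed. The downside is that reported extremes may look less favourable.

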7.3.2. Missing Data

In general, there will be no substitutions made to accommodate missing data points. All data recorded on the case report form (CRF) will be included in data listings that will accompany the clinical study report.

7.3.2.1. Handling of Missing Date Values

Partial or Missing Dates

The following conventions will be used to impute missing portions of dates for adverse events and concomitant medications, if warranted. Note that the imputed values outlined here may not always provide the most conservative date. In those circumstances, the imputed value may be replaced by a date that will lead to a more conservative analysis.

A. Start Dates

- 1) If the year is unknown, then the date will not be imputed and will be assigned a missing value.
- 2) If the month is unknown, then:

- i) If the year matches the first dose date year, then impute the month and day of the first dose date.
 - ii) Otherwise, assign ‘January.’
 - 3) If the day is unknown, then:
 - i) If the month and year match the first dose date month and year, then impute the day of the first dose date.
 - ii) Otherwise, assign the first day of the month.
- B. Stop Dates
 - 1) If the year is unknown, then the date will not be imputed and will be assigned a missing value.
 - 2) If the month is unknown, then assign ‘December.’
 - 3) If the day is unknown, then assign the last day of the month.

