7 STUDY TREATMENTS

7.1 Treatments Administered

All subjects will begin treatment with AERT at 40 mg per day (2 x 20 mg) for 3 days, then increase to 60 mg per day (3 x 20 mg) for 3 days, and then increase to 80 mg per day (4 x 20 mg). Once the subject has reached the maintenance dose, they will remain on that dose for approximately 1 year (Figure 2). The maintenance dose will be the highest tolerated dose, not exceeding 80 mg per day. The description of study drug kits and treatments is shown below in Table 2. Subjects may choose to taper study drug after Visit 3 if they experience adverse events. Direct consultation with the investigator site must be conducted before consideration for dose taper. Dose tapers should occur over the course of 9 days in 20 mg increments. Subjects should be encouraged to titrate back to 80 mg once adverse events subside or remain on the maximally tolerated AERT dose. Up to 3 dose tapers over the course of the clinical study are permitted.

Table 2: Study Drug Kits and Treatments, Study OS440-3005

Dosage form description:	Blue, round biconvex tablets.
Package description:	HDPE white bottles with 60 active 20-mg tablets.
Daily dose:	40, 60, and 80 mg arbaclofen depending on the study day. There will be a 9-day titration period (3 days at 40 mg/day, 3 days at 60 mg/day, and then increase to 80 mg/day), then an approximately 1-year maintenance period at 80 mg/day or the highest tolerated dose, followed by a 2-week taper period. Study tablets will be taken twice daily (BID).
Cumulative maximal dosage:	up to 28,420 mg arbaclofen
Manufacturer:	Osmotica Pharmaceutical US LLC, Marietta, GA 30062

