10. SAFETY ANALYSES

10.1. Adverse Events

The number and percent of subjects with any treatment-emergent adverse events (TEAEs) will be displayed by system organ class and preferred term (MedDRA Version 20.1). Within each preferred term, subjects will be counted only once if they had more than one event reported during the treatment period.

TEAEs will also be summarized by greatest reported severity for each event preferred term. Counts indicate subjects reporting one or more TEAEs that map to the severity grade classification for each preferred term. At each level of summarization (system organ class or event preferred term) subjects are only counted once and the worst severity case of repeated instances of the same TEAE will be used in tabulations. TEAEs will also be summarized by strongest investigator assessment of relationship to study drug in a similar manner.

In addition to the above described analyses, specific AE summaries will be presented under the following conditions:

- TEAEs by SOC/PT will be presented by modal dose within period (titration/dose response, maintenance, and taper period).

- TEAEs by SOC/PT will be presented by dose the subject was on at time of event within period (titration/dose response, maintenance, and taper period).
- All AE summaries will be presented by dose the subject was on at time of event.

Analyses of AEs will be performed for those events that are considered treatment emergent, where treatment emergent is defined as any AE with onset or worsening on or after the first dose of study drug up until last dose of study drug.

Treatment emergent summarization will be characterized by serious or not, the severity and the relationship with the study drug. A conservative approach will be taken to assess the relationship of an AE to study drug; if the relationship of an event is missing, it will be considered treatment-related. Missing severity will be coded as severe.

All TEAEs will be listed individually by subject. In addition, a separate listing will be produced for AEs that are not treatment-emergent.

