12 REVISION HISTORY

Changes from version SAP.00: The SAP was revised and amended to remove the 30 day window for the derivation of treatment emergent adverse events. Adverse events will now be counted as treatment emergent up until the last dose date.

Changes from version SAP.01: The SAP was revised and amended to add additional Adverse event analyses: All AE analyses by dose the subject was on at time of event; TEAEs by SOC/PT by modal dose and period (titration/dose response, maintenance, and taper period); TEAEs by SOC/PT analyses by dose the subject was on at time of event and period (titration/dose response, maintenance, and taper period).

For TNmAS-MAL and TNmAS-TL, the baseline from OS440-3004 will be included as a separate analysis to the planned analyses using the baseline of Visit 6/ET result from Study OS440-3004.

For dose exposure, the total days at each particular dose level have been added to the subject listing and a new summary table counting the total days at each dose level and overall has been included.

For all tables modal dose categories have been changed from < 80 and = 80 mg to modal dose categories of 40 mg, 60 mg, and 80 mg.

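### The partial-date rule for AE onset is safe for the treatment-emergent flag, but in the dose-at-onset and period tables it places such events at 40 mg in titration by default

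*SAP*

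**What the plan says.** SAP 7.3.2.1 introduces the rules as follows: "The following conventions will be used to impute missing portions of dates for adverse events and concomitant medications, if warranted". Three start-date branches matter here.

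- Rule A.2.i, month unknown: "If the year matches the first dose date year, then impute the month and day of the first dose date".
- Rule A.3.i, only the day unknown: "If the month and year match the first dose date month and year, then impute the day of the first dose date".
- Rule A.3.ii, only the day unknown, any other month: "Otherwise, assign the first day of the month".

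A year-only date in a different year goes to January, and an unknown year is left missing. The section concedes that its values may not always be the most conservative, and adds: "In those circumstances, the imputed value may be replaced by a date that will lead to a more conservative analysis".

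On dose, Protocol 7.1 states: "All subjects will begin treatment with AERT at 40 mg per day (2 x 20 mg) for 3 days". Protocol 7.5 sets out nine titration days: three at 40, three at 60 and three at 80 mg/day.

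On tables, SAP 10.1 states: "All AE summaries will be presented by dose the subject was on at time of event". It also plans treatment-emergent events by dose at onset within period, and by modal dose within period. The periods are titration/dose response, maintenance and taper. SAP 12 shows that these displays came in after version SAP.01 ("All AE analyses by dose the subject was on at time of event"). It lists no change to the date rules at that revision.

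**The concern.** One imputed date now does two jobs. For the treatment-emergent flag, the first-dose date is the cautious choice, because a doubtful event is counted as on treatment. For dose and period it is not cautious. It settles the answer at the lowest dose and the earliest period without looking at the subject's dosing record, the event's stop date or the visit at which it was reported.

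The study is meant to supply long-term safety data at 80 mg/day (Protocol 11.3, SAP 6). Most other tables group subjects by modal dose. The dose-at-onset displays are where an event is tied to the dose being taken at the time, so an event wrongly placed at 40 mg is lost from the column that matters most. In the dose-within-period table, the 40 mg titration cell covers only three planned days per subject, so a few misplaced events could visibly change it.

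**Working it through.** The documents give no figure on this point to reproduce, so the check counts days.

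**Inputs from the documents.** 40 mg on Days 1–3, 60 mg on Days 4–6, and the 80 mg step from Day 7; titration is Days 1–9 (Protocol 7.1 and 7.5; 3 + 3 + 3 = 9). Maintenance lasts 52 weeks (Protocol 4.1). Titration plus maintenance is 9 + 364 = 373 days, so a subject on schedule does not reach taper within the calendar year of first dose.

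**Assumptions, not in the documents.** Onset is uniform over the candidate days, and first-dose dates are uniform over a 365-day year.

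**Formulas.** Let D be the number of days from first dose to the end of the known date unit: 31 December under A.2.i, month end under A.3.i.

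- Share at 40 mg = min(3, D)/D
- Share at 60 mg = min(3, max(0, D − 3))/D
- Share on Day 7 or later = max(0, D − 6)/D
- Share in titration = min(9, D)/D

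**Rule A.2.i (year only).**

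| First dose | D | 40 mg | Day 7 or later | In titration |
|---|---|---|---|---|
| 2 January | 364 | 0.8% | 358/364 = 98.4% | 2.5% |
| 1 July | 184 | 1.6% | 178/184 = 96.7% | 4.9% |
| 1 October | 92 | 3.3% | 86/92 = 93.5% | 9.8% |
| 1 December | 31 | 9.7% | 25/31 = 80.6% | 29.0% |
| 22 December | 10 | 30% | 4/10 = 40% | 90% |
| Average over the year | – | 4.6% | 91.7% | 11.5% |

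On average, 100 − 11.5 = 88.5% of candidate days lie outside titration.

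**Rule A.3.i (day missing, first-dose month).** The averages are 31% at 40 mg, 19% at 60 mg and 50% on Day 7 or later; 64% of days lie in titration. With D = 31 the Day-7-or-later share is 80.6%. With D = 15 it is 9/15 = 60%. With D of 6 or fewer it is zero.

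**Sensitivity to early events.** If the daily AE rate in titration is 3, 5 or 10 times the later rate, the average A.2.i share on Day 7 or later falls from 92% to 85%, 80% or 72%.

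**Sensitivity to dose reached.** Day 7 or later does not mean 80 mg. If 50%, 70% or 90% of subjects are at 80 mg from Day 7, the chance that an A.2.i event began on 80 mg is 0.917 × 0.5 = 46%, 0.917 × 0.7 = 64% or 0.917 × 0.9 = 83%. Under A.3.i it is 25%, 35% or 45%.

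**The case against.** **Dose reached.** A reader might infer that these subjects were almost certainly on 80 mg. The documents do not support that. Maintenance is at the highest tolerated dose, up to three dose tapers are allowed (Protocol 7.1), Protocol 7.1.1 foresees subjects maintained at 40 mg, and the SAP plans modal-dose groups of 40 and 60 mg. For a subject who stayed at 40 mg, the assigned dose is right and only the period may be wrong.

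**Day-missing dates.** Under A.3.i the titration label is right more often than not, and a first dose late in the month leaves no candidate day at 80 mg. This stands and limits the point.

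**Rarity.** Protocol 9.7.1 asks subjects at each visit about the time since the last one. Scheduled visits are at most 14 weeks apart, and data inconsistencies are queried (Protocol 15). Year-only dates may therefore be few, and a uniform spread over most of a year is a simplification. This also stands.

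**Direction.** A reader might infer that events move only from 80 mg to 40 mg. Some truly began at 40 or 60 mg. Because AEs are collected from consent (Protocol 9.7.3), some may predate dosing.

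**Small receiving cell.** The three planned days describe only 40 mg within titration. The overall 40 mg column also holds time from subjects maintained at or reduced to 40 mg.

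**Existing safeguard.** The SAP lets an imputed date be replaced by a more conservative one. That is optional and does not say what conservative means for dose. Since the first-dose date is already conservative for the treatment-emergent flag, nothing prompts its use.

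**Consequence.** No tests are planned, all treatment-emergent events are listed by subject, and overall and whole-study modal-dose incidence do not depend on the dose at onset. The harm is confined to the descriptive dose-at-onset and period displays.

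**Conclusion.** The gap is real and follows from the text alone. Rules A.2.i and A.3.i put onset on Day 1, Day 1 is 40 mg in titration, and no other rule assigns dose or period to a partly dated event.

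For year-only dates the assigned dose and period are usually wrong for subjects above 40 mg. About 92% of candidate days fall on Day 7 or later (93–98% when first dose is by 1 October) and about 88.5% fall after titration. These figures assume uniform onset and uniform first-dose dates; heavy early clustering lowers the first to about 72%. For day-missing dates the error is smaller: about half of candidate days fall on Day 7 or later, and about 64% are in titration.

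The effect on the tables cannot be sized. A reader might scale the DSMB trigger in SAP 7.4.2 to about 900/0.75 = 1,200 AEs and apply a partial-date rate to obtain a count. Those triggers schedule meetings and do not forecast AE totals, and the documents give no partial-date rate. The share of subjects at 80 mg is also not given.

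**What to change.** Add to SAP 7.3.2.1 that the imputed start date is used for the treatment-emergent flag only. For the dose-at-onset and period tables:

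1. Bound the onset by the known date parts, the first dose, the AE stop date and the visit at which the event was first reported.
2. Assign dose and period only when the whole interval lies within one dose and one period.
3. Otherwise show the event in a row for dose or period at onset not determinable.
4. Report how many events were affected.

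The reporting visit is useful because subjects are asked about the time since the previous visit. If that visit is taken as the lower bound, an event first reported at Visit 2 began after Visit 1. Visit 1 is at Week 2 ± 3 days, so about Day 14 − 3 = 11 at the earliest, which is already past the nine titration days. Without such a lower bound the interval starts at Day 1, and most of these events will go to the extra row. This assumes that the reporting visit can be recovered from the AE records.

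Assigning the highest dose in the interval is not recommended. It would replace a bias towards 40 mg with one towards 80 mg, and the period would stay unclear because 80 mg occurs in both titration and maintenance.

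The cost is a short SAP addition, one extra table row and minor programming.

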8.5. Prior and Concurrent Medications

The number and percentages of all concomitant medications will be summarized, Anatomical Therapeutic Chemical (ATC) level 4 and PT. The total number of concomitant medications and the number and percentages of subjects with at least 1 concomitant medication will be summarized.

The number and percentages of all prior medications will be summarized similarly to concomitant medications in a separate table.

A concomitant medication is defined as any medication taken on or after the day of first dose of study drug. The prior medications are defined as any medication that starts and ends prior to the first dose of study drug.

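### The SAP's partial-date rules move a start date to the first dose without checking a known stop date, so an AE that resolved before dosing can be counted as treatment-emergent

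*SAP*

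**What the plan says.** SAP 7.3.2.1 gives three rules for incomplete start dates of AEs and medications.

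- Year unknown (A.1): "If the year is unknown, then the date will not be imputed and will be assigned a missing value".
- Month unknown (A.2.i): "If the year matches the first dose date year, then impute the month and day of the first dose date". If the year differs, January is assigned.
- Day unknown (A.3.i): "If the month and year match the first dose date month and year, then impute the day of the first dose date". If the month or year differs, the first of the month is assigned.

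None of these start-date rules mentions the stop date. The section applies them where warranted, and concedes that an imputed value may not be the most conservative one: "In those circumstances, the imputed value may be replaced by a date that will lead to a more conservative analysis". It gives no criteria for doing so.

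These dates feed two classifications. In SAP 10.1, "treatment emergent is defined as any AE with onset or worsening on or after the first dose of study drug", with last dose as the upper limit. The same section says "Analyses of AEs will be performed for those events that are considered treatment emergent", and that "a separate listing will be produced for AEs that are not treatment-emergent". In SAP 8.5, "The prior medications are defined as any medication that starts and ends prior to the first dose of study drug", while a concomitant medication is one taken on the day of first dose or later.

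**The concern.** Records that end before dosing exist by design. Protocol 9.7.3 has AEs reported from informed consent. De novo subjects consent at a Screening visit up to 21 days before Baseline and withdraw their anti-spasticity drugs in that interval (Protocol 6.1). Their medications over the 30 days before Baseline are recorded (Protocol 7.7).

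For such a record, a stop date before first dose settles the matter: the AE is not treatment-emergent and the drug is prior. The imputation rule overrides that information and produces an impossible interval, with the start after the stop. Safety is the primary objective and the treatment-emergent tables are its main output, so a rule that places a resolved washout event in those tables should be corrected. The gaps also mean that two programmers following the same text could classify the same record differently.

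**Working it through.** The plan states no figure on this point. I applied rules A.1 to A.3 literally to example records, then worked out how often the first-dose date would be assigned.

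**Examples** (first dose assumed to be 2018-06-20)

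| Record | Imputed start | Result |
|---|---|---|
| AE, June 2018, day unknown, stopped 2018-06-12 | 2018-06-20 | Start 8 days after stop; meets the treatment-emergent onset test |
| AE, 2018, month unknown, stopped 2018-06-12 | 2018-06-20 | Same |
| Baclofen, 2018, month unknown, stopped 2018-06-18 | 2018-06-20 | Start 2 days after stop; not prior by its start, not concomitant by its stop |
| Baclofen, March 2018, day unknown, stopped 2018-06-18 | 2018-03-01 | Prior, correct |
| Baclofen, 2015, month unknown, stopped 2018-06-18 | 2015-01-01 | Prior, correct |
| AE, year unknown | Missing | Onset test cannot be evaluated |

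**AEs: share moved to the first-dose date**

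Assumptions: true onset is uniform over days 1 to 21 before first dose (the protocol's maximum washout; SAP 5.1 still describes at least 21 days), and the event resolved before dosing.

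- *Day missing.* If first dose falls on day d of a 30-day month, min(d − 1, 21) of the 21 preceding days lie in the same month. Days 1 to 22 contribute 0 + 1 + … + 21 = 231. Days 23 to 30 contribute 8 × 21 = 168. The share is (231 + 168) / (30 × 21) = 399 / 630 = 63.3%. Enumerating all 365 first-dose days of a calendar year gives 4,893 / 7,665 = 63.8%.
- *Month missing.* Only onsets in the previous calendar year escape. These arise for first doses on 1 to 21 January and number 21 + 20 + … + 1 = 231. The share is (7,665 − 231) / 7,665 = 97.0%.

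**Washed-out anti-spasticity drugs**

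Inclusion criterion 6 requires a regimen stable for at least 1 month before Baseline, so I took starts at least 31 days before first dose.

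- *Day missing.* A start 31 or more days earlier cannot share the first-dose month, so the share is 0%.
- *Month missing.* The share depends on how far back starts reach, again assuming uniform timing:
  - last 1 year: 55,945 / 122,275 = 45.8%
  - last 2 years: 55,945 / 255,500 = 21.9%
  - last 5 years: 55,945 / 655,175 = 8.5%

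All these shares are conditional on the start date being partial in the stated way.

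**With a stop-date check.** Capping the imputed start at the known stop moves the AE examples to 2018-06-12 (not treatment-emergent) and the third record to 2018-06-18 (prior). The cap does nothing for an unknown year, which needs its own default.

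**The case against.** The best defence is that the section leaves room for judgement: imputation happens only where warranted, and a value may be replaced by a more conservative one. A careful programmer would see that a stop before first dose makes an imputed start unnecessary. That is fair as a prediction, but neither clause states a rule. For AEs, the more conservative choice would normally keep the event as treatment-emergent, so the override does not correct the error. It also covers imputed values, and an unknown-year start is not imputed.

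A second defence is that over-counting AEs is the safe direction in a safety study. That holds when timing is uncertain. When the stop date is known to precede first dose, it is not.

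A third is that few subjects are exposed. This stands. For rollover subjects, consent, Baseline and first dose share one visit (Protocol 6.2), so washout-phase AEs arise only in de novo subjects. SAP section 6 expects up to 50 of these among about 300 (50 / 300 = 17%), although the protocol states no cap.

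Three stronger readings are tempting, but the documents do not support them.

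- A reader might infer that washed-out drugs will be reported as prohibited use on study. SAP 8.5 makes a drug concomitant only if taken on or after the day of first dose, and a known earlier stop rules that out. The text leaves the drug between classes. Only an unknown month with a start in the first-dose year produces this.
- A reader might infer that AEs with no start year are lost. No passage declares them non-treatment-emergent. Protocol 11.5 refers to events reported from first dose onward, SAP 7.3.2.2 defaults conservatively for missing severity and relationship, and all collected data are listed. An unknown year should also be rare when AEs are asked about at every visit.
- A reader might infer that deviation or withdrawal counts would be affected. Nothing derives either from imputed dates.

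**Conclusion.** The defect is real and minor. Followed as written, A.2.i and A.3.i give a start after a known stop and make a resolved washout-phase AE treatment-emergent. For drugs, the outcome is a record that neither definition covers. For unknown-year starts, it is a record that cannot be shown to meet the treatment-emergent definition and has no stated default.

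Among AEs that began 1 to 21 days before dosing and resolved before it, with only the day missing, about 63% would be moved. That rests on uniform timing. The absolute number cannot be estimated because the documents give no rate of partial dates. The analysis is descriptive, so no test or sample size is affected.

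**What to change.** Add two fixed rules to SAP 7.3.2.1, to apply ahead of the discretionary replacement clause:

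(a) An imputed start may not be later than a known stop date. A record whose known stop precedes first dose is classed as pre-treatment (AE) or prior (medication).

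(b) An AE or medication whose start is wholly missing is classed as treatment-emergent or concomitant unless its stop date precedes first dose.

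The cost is a few lines of SAP text and one derivation check for starts later than stops. No new data are needed.
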